
(1) The Progress of Study and Safety of Participants: The Data Safety Monitoring Plan (attached) has been modified to be congruent with the study protocol. Since there is no upper limit for HBA1c, an increase in HBA1c of 3% or more will be monitored. The following data will be examined to evaluate safety issues: adverse events, attrition rates, reasons for attrition, and rates of adherence to treatment intervention at all contact points. In order to provide a level of protection to all study subjects, the following will be specifically included for monitoring and follow-up: (1) number (if any) of patients who had suicidal ideation during the course of the study, and adherence to safety protocol (2) number (if any) of patients who have experienced a 30% increase in the CES-D score and recommendations by [name] for follow-up and referral (3) number (if any) of patients who began medication for mental health or sought additional therapy. (4) number (if any) patients who had hypercalcemia or vitamin D levels greater than 100 ng/dl or symptoms of vitamin D toxicity and recommendations by [name].

(2) Compliance with the reporting of adverse events: Determining whether all adverse events and/or unanticipated problems were reported in writing to Loyola University Medical Center within 48 hours of discovery of the incident.

(3) Data Accuracy and Protocol Compliance: Evaluating records for the training of personnel and other protocol documents as needed. All staff personnel will be required to have human subjects training, HIPPA training, and training on all study protocols (Appendix). [name] will have weekly meetings with the project staff and co-investigators. She will also train the staff personnel regarding all procedures (phone as well as in-person protocol), and meet with them as they facilitate the recruitment of study participants and schedule them for data collection. Training will also be provided for the research nurse on the use of the C-DIS. [name] will observe phone as well as on-site screening to ensure that the protocol is being followed, and provide feedback. At baseline, three and six month data collection points, the following will be done by [name] and the staff to ensure protocol compliance: 1) reviewing the informed consent and HIPPA documents; 2) checking questionnaire booklets for missing data prior to study subjects leaving the data collection site; 3) running standards for the hemoglobin A1c prior to subject testing in order to ensure the accuracy of the lab test. [name] will obtain reproducibility data from off-site labs during the times that study specimens are processed.

D. Potential Benefits of the Proposed Research to the Subjects and Others.

At this time, preliminary data from the pilot study suggests that vitamin D may be beneficial for improvement of depressive symptoms. However, given the need for a randomized clinical trial to determine whether the pilot data will substantiate these findings, at this time it is unknown if women will benefit from participating in the study. To our knowledge, there are no studies that have examined whether treating persons with diabetes for depressive symptoms using vitamin D supplementation. Therefore, our study will serve as a new and important contribution to our understanding of whether improvement of their nutritional state by vitamin D supplementation can be effective in improving both mental and physical outcomes. Practice initiated interventions to improve the quality of care for depression management in patients with diabetes may also substantially increase the welfare of these patients, particularly as it relates to their own self-management, however, this has not been well studied either.

E. Importance of the Knowledge to be Gained. Given the high cost of treating depression, its prevalence in persons with diabetes, particularly women, studying the benefit of vitamin D supplementation for this group has significant impact. With an improvement in depression, there may be an improvement in self-care behaviors which is also being examined and has not been well studied relative to depression. Finally, studying vitamin D supplementation for the effects on blood pressure also has important clinical implications as research examining this outcome is limited. In clinical studies that have explored vitamin D and mood outcomes (other than Jorde et al.) the amount of vitamin D has been low, the duration of supplementation short, and blood levels were not measured (23). The proposed study is unique in that the amount of vitamin D to be administered is currently what is recommended for obese individuals (34), thus the translation of study findings to practice is significant. The most important benefit of vitamin D supplementation if effective, is its low cost (as low as \$3 per month) and affordability to the general public. Given its low cost, association with minimal side effects (36), that 1 in 10 Americans now take antidepressants which can have negative effects on weight and metabolic control (100), that depression is higher in women than men (7) especially in diabetes, this study can benefit the general public.

Inclusion of Women and Minorities Depression occurs more often in women with diabetes than men with diabetes, and over 25% of women with diabetes have depression (7). It has been reported that depression is associated with poorer diet, physical activity and medication adherence for women with diabetes (6, 72-76). Having both diabetes and depression is associated with a significantly increased risk for complications, including cardiac mortality which occurs more often in women with type 2 diabetes (53). The Women's Health Initiative (WHI) reported that low vitamin D intake was associated with significant depressive symptoms (27). Preliminary data has suggested it has a potential benefit for depression treatment for women (33). The Nurses' Health Study reported that women were twice as likely to develop hypertension if vitamin D levels were less than 15 ng/ml (83). Pfeifer and colleagues (91) reported a 7% decrease in systolic blood pressure in

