The Nurses' Health Study reported that women were twice as likely to develop hypertension if vitamin D levels were less than 15 ng/ml (83). Women have vitamin D levels as low as 15-20 ng/ml (84, 85), especially those with type 2 diabetes (86). There have been few vitamin D trials in women to examine blood pressure effects, and results have been inconsistent (87-89). The Women's Health Initiative did not find a change in blood pressure with vitamin D supplementation; however, the dose (400 IU) daily may not have been sufficient (90). Yet Pfeifer and colleagues (91) did report a 7% decrease in systolic blood pressure in vitamin D deficient women following 800 IUs of vitamin D₃ after 6 weeks.

High blood pressure is a major risk factor for persons with diabetes which contributes significantly to their renal complications. Epidemiologic evidence indicates that low levels of vitamin D are associated with a higher systolic blood pressure (92). Because persons with diabetes are at high risk for hypertension, this outcome is important in assessing as an additional benefit of vitamin D supplementation. In addition, because depression increases the risk for hypertension and stroke, this is another important reason for its study (37-39). Thus, we propose that vitamin D supplementation will decrease systolic blood pressure (Figure).

Vitamin D and Diabetes. Our pilot study did not demonstrate improvements in glycemic control following vitamin D supplementation; although women had type 2 diabetes for an average of 8 years and were under good metabolic control (see pilot data). Some epidemiologic evidence suggests that vitamin D may prevent diabetes (93, 94), however, few RCTs are published (95, 96). The Women's Health Initiative reported that that vitamin D did not prevent the development of type 2 diabetes (97). Other studies have been inconclusive regarding the effects vitamin D supplementation on glycemia, with most showing no significant benefit (98, 99).

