d. Treatment side effects. Published reports suggest that 50,000 IU per day of vitamin D (note that the proposed study dose is 50,000 IU per week) can increase vitamin D levels to more than 150 ng/dl and cause hypercalcemia (35). The current dose for this study is one capsule of 50,000 IU per week which equates to about 7000 IU per day. The dose at which the Vitamin D is being administered has minimal side effects, which may include gastrointestinal symptoms of constipation, stomach upset, and loss of appetite. Symptoms associated with vitamin D toxicity include bone pain, nausea, and vomiting (35, 120). We will be monitoring patient labs and for these symptoms at all study visits (baseline, 3, 6 months). Telephone interview (months 2, 4) will be used when patients are not seen for these assessments as with our pilot study (see procedures).

e. Safety. The vitamin D levels will be sent to the endocrinologist who will monitor the labs for the study, and inform the PI if the supplement needs to be stopped. This will be done when a study subject has either: (1) hypercalcemia or (2) vitamin D level of greater than 100 ng/ml with normal serum calcium or symptoms of vitamin D previously listed that may be indicative of possible toxicity (35). Patients will be requested to return for a serum level of vitamin D within one month (since the half life is approximately two weeks) of stopping therapy (120) and then again at the end of the study. The depression assessment will be reviewed with the psychiatrist prior to enrollment and subjects will be monitored for depression over the course of the study when they are seen (baseline, 3, 6 months) as well as when they are not seen (months 2, 4) by telephone. Subjects will be withdrawn if there is significant worsening of depression (see Human Subjects). These protocols were followed for the pilot study and no adverse effects occurred.

2. Sample.

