a. Criteria for Participation. Inclusion criteria are: 1) women aged 21 and older, 2) having significantly elevated depressive symptoms as measured by a score \geq 16 using the Center for Epidemiologic Studies Depression Tool (CES-D) (118,121) and/or taking antidepressant medication and having a score \geq 12 using the CES-D and/or CES-D score average of \geq 16 of phone screen and face to face screen, 3) type 2 diabetes and under the care of a health care provider, (4) level of vitamin D also known as 25 hydroxyvitamin D, 25 (OH) D less than 32 ng/dl. **Exclusion criteria are:** 1) current alcohol or substance abuse disorders, 2) a history of bipolar depression or any other psychotic disorder, 3) debilitating chronic illness (e.g., cancer, multiple sclerosis), 4) severe complications of diabetes (e.g., blindness or amputation) since these will impact depression, 5) malabsorption disorders (e.g., crohn’s disease, celiac sprue, gastric bypass) since this impacts vitamin D absorption (122), 6) elevated serum calcium since vitamin D may increase serum calcium (123). 7) taking St. John’s Wort unless they stop for 3 weeks prior to enrollment since it can impact mood (124). 8) use of vitamin D supplements (1000 IUS or greater) in past 2 months and unwillingness to discontinue for at least 1 month prior to study 9) Pregnant or planning a pregnancy. 10) Baseline systolic blood pressure greater than 160 mmHG or diastolic greater than 100 mmHG. Having active treatment for depression (e.g., antidepressant therapy) will not be exclusion criteria if the patient has been under treatment for six weeks or more. Similar criteria were used for our pilot.

b. Recruitment. We contacted diabetes centers within a 20 mile radius of LUMC (most are within a 5 to 10 mile radius) with the closest facilities. The diabetes educators provided estimates of potential patients with type 2 diabetes per month. Support letters have been provided by the recruitment sites. To facilitate recruitment, a meeting will be held at each site (with educators and endocrinologists) to discuss the study, review study brochure, procedures for participating, and follow-up information. We used these sites and this recruitment strategy for our pilot and SWEEP study. We will also work with our marketing department for recruitment of study participants.

Diabetes Center Sites	# Patients/Mo	Diabetes Center Sites	# Patients/Mo

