Prior to leaving the data collection site, the participants will be asked to partake in a brief history and physical that will be conducted by a trained health care professional. This assessment will take 20 minutes.

c. Study Visits. Following the first visit, the lab tests (vitamin D, calcium, PTH, Cardiometabolic profile as recommended by the FDA) will be reviewed by [name], endocrinologist and co-investigator to ensure that blood enrollment criteria are met. If so, the patient will be scheduled for a second visit within 10 days of their initial visit. At that visit, the patient will have a body composition scan to assess for body composition (which includes bone, lean and fat mass) which should take 30 minutes. Prior to the scan, a pregnancy test will be administered to ensure the subject is not pregnant (see human subjects). Upon completion, a small conference room at that site will be used for the research nurse to provide the study supplement, review the weekly schedule, and discuss all subsequent contacts (phone and scheduled visits). The study nurse will also review potential side effects and reiterate the reproductive risks associated with the treatment at baseline visit 2 and 3 month visit when the supplement is provided. The patient will be told that an automated message (preferred as phone, e-mail or text) will remind them to take their weekly supplement. They will be informed that at three and six months, they will return for data collection of physical measurements and questionnaires. They will be told that in the months (2, 4,) when they don't have a scheduled visit, the study nurse will conduct a formal phone call follow-up where they will be asked about their compliance, side effects, and be screened for their depressive symptoms (CES-D). These procedures will be followed for all phone call visits (Appendix).

Upon completion of these verbal and written instructions, the supplement will be dispensed. There will be a total of 12 pills for the period of 12 weeks. Following the dispensing directions, the nurse will ask the subject if they have any questions to ensure there is an understanding and to call the study nurse if questions arise.

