7. Timeline. We have proposed a timeline of four years with the enrollment of 180 in the treatment arms and follow-up of all women completed by Year 4. For year 1, time is committed for start up, enrollment and start of intervention. We plan to enroll 50 subjects into the treatment arms in year 1. For years 2 and 3 we will plan to enroll 65 each year into the treatment arms. We will complete intervention delivery by the third month of year 4 with follow-ups complete by the sixth month of that year. Final data analysis and reports will be completed by the end of Year 4.

VI. PROTECTION OF HUMAN SUBJECTS.

A. Risks to the Subjects

(1) Human Subjects Involvement and Characteristics. We will enroll a total of 360 women to allow for attrition and screen failure over the course of the study (our pilot study had an attrition of 8%). Women 21 and older with a depression score of CES-D ≥ 16 and/or taking antidepressant medication with a CES-D depression score of ≥ 12 and/or CES-D score average of ≥ 16 of phone screen and face to face screen, and type 2 diabetes who are under the care of a health care provider will be recruited. They must also have a vitamin D level of less than 32 ng/ml verified by laboratory testing.

Participants will be excluded if they have: 1) current alcohol or substance abuse disorders, 2) a history of bipolar depression or any other psychotic disorder, 3) debilitating chronic illness (e.g., cancer, multiple sclerosis), 4) severe complications of diabetes (e.g., blindness or amputation) since these will impact depression, 5) malabsorption disorders (e.g., crohn's disease, celiac sprue, gastric bypass) since this impacts vitamin D absorption (122), 6) Elevated serum calcium since vitamin D may increase serum calcium (123). 7) Taking St. John's Wort and not willing to stop for 3 weeks prior to enrollment) (124), 8) Use of vitamin D supplements in past 2 months and unwillingness to discontinue for 1 month prior to study 9) Pregnant or planning a pregnancy. 10) Baseline systolic blood pressure greater than 160 mmHG or diastolic greater than 100 mmHG. Having active treatment for depression (e.g., antidepressant therapy) will not be exclusion criteria if the patient has been under treatment for six weeks or more. Similar criteria were used for our pilot.

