There is the potential that patients may become depressed over the course of the study. If patients demonstrate significant increases in the depression scores (i.e., an increase of 30% or more), either Drs. [name] or [name] will be consulted, and a determination will be made regarding contact with the primary care provider and a referral to a mental health care provider (HIPPA signed, see protection against risks). This will be done for those in treatment and control group at all points of contact (phone or face to face). If during the course of the study patients begin any medication for mood (e.g., depression or anxiety), this information will be recorded. If the patient begins therapy during the course of the study, the therapist will be contacted to ensure that the study does not conflict with the patient's current treatment protocol.

Hypercalcemia is a potential side effect of persons taking higher doses of vitamin D and this lab will be monitored to ensure that it is not present at time of enrollment and does not increase over the course of the study by the endocrinologist. Most recent evidence demonstrates that hypercalcemia may not be a significant side effect associated with vitamin D (49). Vitamin D levels will be measured at baseline to ensure that the level is less than 32 ng/ml. It will also be monitored over the course of the study to ensure that the levels do not increase or that there are symptoms of toxicity. Safety procedures are listed (see protection against risks).

To decrease the possibility of hypoglycemia from fasting, patients will be asked to make sure that they eat a protein before bedtime and bring their morning diabetes medications to take with the breakfast that is provided. For persons taking insulin, they will be informed that if they take insulin in the evening, to contact their health care provider about the dose that they should take when fasting for morning blood draws. They will also be informed to bring their morning medications to their data collection visits to take with their breakfast.

B. Adequacy of Protection Against Risks.

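### Two operative vitamin D limits, the safety board's counting threshold and the inclusion limit, are written in ng/dl where ng/ml is meant, a 100-fold error in each

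*Combined protocol and SAP*

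**What the plan says.** **Safety limit.** Section VI.C(1), item (4), lists among the matters the safety board monitors the number of "patients who had hypercalcemia or vitamin D levels greater than 100 ng/dl or symptoms of vitamin D toxicity". The rule for stopping the supplement, given in V.1.e (Safety) and repeated in VI.B(2) (Protection Against Risks), includes a "vitamin D level of greater than 100 ng/ml with normal serum calcium".

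**Entry limit.** Section V.2.a (Criteria for Participation) requires "25 hydroxyvitamin D, 25 (OH) D less than 32 ng/dl". Section VI.A(1) says: "They must also have a vitamin D level of less than 32 ng/ml verified by laboratory testing". Section VI.A(3) says: "Vitamin D levels will be measured at baseline to ensure that the level is less than 32 ng/ml".

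**Attached plan.** Section VI.C(1) also states: "The Data Safety Monitoring Plan (attached) has been modified to be congruent with the study protocol". The attachment is not part of the text available for this review.

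**Background figure.** Sections V.1.d and VI.B(2) cite a published toxicity level of 150 ng/dl at a dose of 50,000 IU per day. This is supporting text and not a limit that anyone applies in the trial.

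**The concern.** The same two numbers, 100 and 32, appear with units that differ by a factor of 100. One is a threshold for safety reporting and the other decides who may enter, so each should be correct where it is used.

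Section V.2.a is the main eligibility list. Against its literal wording, essentially every randomized woman would be a protocol deviation. Section VI.C(1) defines what the board counts as a possible vitamin D toxicity signal. A literal count would include nearly all participants and so could not single out the women whose supplement should be stopped. The board's criterion should also match the rule that stops treatment, so that the board sees the cases the rule is meant to catch.

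**Working it through.** **Inputs**

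| Item | Where | As written |
|---|---|---|
| Board's counting threshold | VI.C(1), item (4) | 100 ng/dl |
| Stopping rule | V.1.e and VI.B(2) | 100 ng/ml |
| Inclusion limit | V.2.a | 32 ng/dl |
| Inclusion limit | VI.A(1) and VI.A(3) | 32 ng/ml |
| Low levels reported in women | I. Significance | 15–20 ng/ml |
| Pilot inclusion limit | IV. Preliminary Studies | below 30 ng/ml |
| Pilot levels, mean (SD): baseline, 3 months, 6 months | IV. Preliminary Studies | 18.78 (7.0), 34.39 (9.4), 37.5 (9.5) ng/ml |
| Women randomized of those enrolled so far | V.5.d | 83 of 169 |

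**Step 1: convert.** 1 dl = 100 ml, so x ng/dl = x/100 ng/ml.

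- Board: 100/100 = 1 ng/ml, against 100 ng/ml in the stopping rule. Ratio 100.
- Entry: 32/100 = 0.32 ng/ml, against 32 ng/ml elsewhere. Ratio 100.

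**Step 2: compare the literal limits with levels the protocol reports.**

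- Section I says "Women have vitamin D levels as low as 15-20 ng/ml". Those levels are 15/1 = 15 to 20/1 = 20 times the literal board threshold, and 15/0.32 = 46.9 to 20/0.32 = 62.5 times the literal entry limit.
- The pilot baseline mean is 18.78/0.32 = 58.7 times the literal entry limit.

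**Step 3: approximate the share of women affected.** This assumes normal distributions with the pilot means and SDs. The pilot gave 50,000 IU weekly, so its follow-up values bear on the high-dose arm only. The protocol gives no levels for the 5000 IU arm.

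- Above 1 ng/ml at baseline: z = (1 − 18.78)/7.0 = −2.54, share 99.4%.
- Above 1 ng/ml at 3 months: z = (1 − 34.39)/9.4 = −3.55, share 99.98%.
- Above 1 ng/ml at 6 months: z = (1 − 37.5)/9.5 = −3.84, share 99.99%.
- Below 0.32 ng/ml at baseline: z = (0.32 − 18.78)/7.0 = −2.64, share 0.42%. Of this, 0.36% lies below zero (z = −18.78/7.0 = −2.68), which no real level can be. The true share is therefore close to nil.

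**Step 4: repeat with ng/ml.**

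- Above 100 ng/ml: z = (100 − 34.39)/9.4 = 6.98 at 3 months and (100 − 37.5)/9.5 = 6.58 at 6 months. The share is effectively zero, as a toxicity threshold should give.
- Below 32 ng/ml: every pilot woman entered with a level below 30 ng/ml, so all would have met this limit.

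**Step 5: check against conduct.** Section V.5.d reports 83/169 = 49.1% randomized. An entry limit of 0.32 ng/ml could not have produced that.

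Only the ng/ml reading is workable for either limit.

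**Background figure.** 150 ng/dl = 1.5 ng/ml, which is below the pilot baseline mean of 18.78 ng/ml and so cannot be a toxic level. It is probably the same slip, but the protocol nowhere gives this figure in ng/ml.

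**The case against.** The best reply is that this is a typing slip with one sensible reading. Each limit is stated correctly twice elsewhere, and the literal values are so low that staff would notice them before acting on them.

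The control that protects participants is also right. The stopping rule is in ng/ml in both places, and an endocrinologist reviews the baseline laboratory results ("endocrinologist and co-investigator to ensure that blood enrollment criteria are met") and those at 3 months. Sections V.1.d and VI.B(2) commit to laboratory monitoring at baseline, 3 and 6 months. Item (4) of VI.C(1) is a tally for a committee that meets twice a year and includes vitamin D and endocrinology experts. It stops nobody's treatment. The attached plan may already have the right unit. No sample size, power figure or analysis depends on either limit, and the recruitment figures show that the literal entry limit was not applied.

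All of that stands, and it keeps the point at low priority. It does not make the text correct. The errors sit in the main eligibility list and in the definition of what the board counts. The statement that the attached plan was aligned with the protocol leaves two possibilities: the plan may be right, or the wrong unit may have been carried into it. Only a look at the attachment will tell.

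**Conclusion.** The concern holds. Two current, operative limits are wrong as written, each by a factor of 100: the board's vitamin D threshold (literally 1 ng/ml, should be 100 ng/ml) and the inclusion limit (literally 0.32 ng/ml, should be 32 ng/ml). The contradiction and the conversion need no assumption. That ng/ml is the intended unit follows from the protocol's other statements, its pilot data and its recruitment to date. Only the percentages rest on the normal approximation to the pilot values, and the conclusion does not depend on them.

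Nothing in the documents shows that a participant, an eligibility decision or an analysis has been affected. This is an inconsistency of units that is worth correcting, and it should rank below any design or analysis issue. Which unit the board actually uses cannot be determined from the text available.

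**What to change.** - In V.2.a, change the inclusion limit to below 32 ng/ml, to match VI.A(1) and VI.A(3).
- In VI.C(1), item (4), change the threshold to above 100 ng/ml, to match V.1.e and VI.B(2).
- Confirm that the attached Data Safety Monitoring Plan uses 100 ng/ml.
- Check the 150 ng/dl figure in V.1.d and VI.B(2) against its cited source and correct it if it proves to be the same slip.

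The cost is two unit corrections, one look at the attachment and one source check. Design, sample size and analysis are unchanged.
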